15.2.3.2 Immune-Related Adverse Events

Immune-related adverse events (irAEs) will be identified programmatically. AEs which satisfy all of the following criteria will be flagged as immune-related:

- 1) The AE PT matches a PT on the list of pre-selected MedDRA terms.
 - 2) The AE onset or worsening occurs from the first study intervention to the last study intervention date + 90 days, death OR to the earliest date of subsequent anticancer therapy minus 1 day, whichever occurs first, unless otherwise stated.
 - 3) On the “Adverse Events Details” eCRF page, the question “Were Corticosteroids, Immunosuppressants, or hormonal therapy (e.g. Thyroid) or Insulin applied?” has the answer “Yes” selected.
 - 4) On the “imAE Specific Questions” eCRF page, either:
 - a. The question “Does any of the following provide a clear etiology for the event?” has the answer “No” selected, indicating that the AE is not attributable to underlying cancer disease/PD, prior or concomitant medications/procedures, nor another medical condition such as an infection or pre-existing disease.
- OR
- b. The “imAE Specific Questions” eCRF page indicates that a biopsy was performed and the question “Is the histopathology/biopsy consistent with an immune-mediated event?” has the answer “Yes” selected.

In the case that criteria (1) through (3) are met, and entries for condition (4) are missing, the following rules will be applied:

- If the answer to “Does any of the following provide a clear etiology for the event?” (4a) is missing, the event will be considered as irAE (irrespective of biopsy results).
- If the answer to “Is the histopathology/biopsy consistent with an immune-mediated event?” (4b) is missing, or if no biopsy was performed, and condition (4a) is not satisfied, i.e. “Yes” is selected (i.e. at least one (clear) etiology of the event is provided) as the answer to the question “Does any of the following provide a clear etiology for the event?”, the event will be considered as a non-irAE.

PTs will be compiled into categories: Immune-mediated rash, Immune-mediated colitis, Immune-mediated pneumonitis, Immune-mediated hepatitis, Immune-mediated nephritis and renal dysfunction, Immune-mediated endocrinopathies (Adrenal insufficiency, Hypogonadism, Pituitary dysfunction, Type 1 Diabetes Mellitus, Thyroid disorders), Other immune-mediated myositis, Other immune-mediated adverse events. PTs belonging to the category “Immune related endocrinopathies – Thyroid disorders” will also be compiled into sub-subcategories: Hyperthyroidism, Hypothyroidism, Thyroiditis.

Immune-related adverse events (irAEs) will be summarized by the following variables:

- Any irAEs
- irAEs by the worst grade
- irAEs leading to permanent treatment discontinuation

- Serious irAEs

The frequency table of immune-related AEs by worst grade, category, subcategory (for Immune-mediated endocrinopathies), sub-subcategory (for Immune-mediated endocrinopathies – thyroid disorders) and PT will also be provided.

The listing of irAE will also be provided with the relevant information, including additional interventions for irAE (e.g. biopsies, surgical procedures, medical procedures) (see description of listing in Section 15.1.1).

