6.9.2 Immune-related Adverse Events

Immune-related AEs are specific to immunotherapies and vary by organ system. Immune-related AEs are considered AESIs.

In general, the spectrum of irAEs is similar for bintrafusp alfa compared with other checkpoint inhibitors. Effective risk management of these toxicities (irAEs) primarily caused due to inhibition of PD-L1 and PD-1 pathways, is based on key recommendations ([Champiat 2016](#)). Participant education for on-time reporting of symptoms of potential irAEs and prompt clinical assessment is critical for effective management and quicker resolution of immune-mediated toxicities, thus

preventing progression into severe forms of toxicity that otherwise may become life-threatening and difficult to manage or warrant permanent discontinuation from the study.

The following irAEs are important identified risks for bintrafusp alfa:

- Immune-related hepatitis
- Immune-related pneumonitis
- Immune-related colitis
- Immune-related nephritis and renal dysfunction
- Immune-related endocrinopathies (thyroid disorders, adrenal insufficiency, type 1 diabetes mellitus, pituitary disorders)
- Immune-related rash
- Other immune-related events (myositis, myocarditis, encephalitis)

The following irAEs are important potential risks for bintrafusp alfa:

- Guillain-Barré syndrome
- Uveitis
- Pancreatitis
- Myasthenia gravis/myasthenic syndrome

The Medical Monitor may be involved as needed for follow-up. Details of the diagnostic work-up will be requested by the study team.

Recommended guidance and management for specific irAEs as per published guidelines as provided in [Appendix 5](#). These recommendations are in accordance with the joint American Society of Clinical Oncology (ASCO) Clinical Practice Guidelines ([Brahmer 2018](#)) and National Comprehensive Cancer Network ([NCCN 2018](#)) guidelines.

Treatment of irAEs is mainly dependent upon severity as defined by NCI-CTCAE v5.0. In general, management by NCI-CTCAE v5.0 grading is listed below:

- Grade 1: study intervention should be continued with close monitoring, with the exception of some neurologic, hematologic, and cardiac toxicities.
- Grade 2: study intervention may be suspended for most Grade 2 toxicities, with consideration of resuming when symptoms revert to Grade 1 or less. Corticosteroids may be administered (initial dose of 0.5 to 1 mg/kg/day of prednisone or equivalent).

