2.0 GI Toxicities	
2.2 Hepatitis	

Definition: A disorder characterized by a viral pathologic process involving the liver parenchyma
 
Diagnostic work-up
 
Monitor patient for abnormal liver blood tests: AST, ALT, and bilirubin prior to each infusion and/or weekly if G1 liver function test elevations. No treatment is recommended for G1 liver function test abnormality
 
For G2 or higher:
 
Work-up for other causes of elevated liver enzymes should be tested, viral hepatitis, alcohol history, iron study, thromboembolic event, liver ultrasound, cross-sectional imaging for potential liver metastasis from primary malignancy. If suspicion for primary autoimmune hepatitis is high, can consider ANAs, antismooth muscle antibodies, antineutrophil cytoplasmic antibodies. If patients with elevated alkaline phosphatase alone, g-glutamyl transferase should be tested. For isolated elevation of transaminases, consider checking CK for other etiologies
	
Grading	Management
All patients	
Counsel all patients to be aware of and inform their health care provider immediately if they experience:
 
Yellowing of skin or whites of the eyes Severe nausea or vomiting
 
Pain on the right side of the abdomen Drowsiness
 
Dark urine (tea colored)
 
Bleeding or bruising more easily than normal Feeling less hungry than usual

G1: Asymptomatic (AST or ALT > ULN to 3.0 x ULN and/or total bilirubin > ULN to 1.5 x ULN)	
Continue ICPI with close monitoring; consider alternate etiologies
 
Monitor laboratories one to two times weekly
 
Manage with supportive care for symptom control

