4.1.2 Hyperthyroidism	

Definition: Suppressed TSH and high normal or elevated FT4 and/or triiodothyronine
 
Diagnostic work-up
 
Monitor TSH, FT4 every 4-6 weeks from the start of therapy or as needed for case detection in symptomatic patients
 
Consider TSH receptor antibodies if there are clinical features and suspicion of Grave disease (e.g., ophthalmopathy)
 
Close monitoring of thyroid function every 2-3 weeks after diagnosis to catch transition to hypothyroidism in patients with thyroiditis and hyperthyroidism
	
Grading	Management
G1: Asymptomatic or mild symptoms	
Can continue ICPI with close follow-up and monitoring of TSH, FT4 every 2-3 weeks until it is clear whether there will be persistent hyperthyroidism (see below) or hypothyroidism (see 4.1.1)
 
Consider holding ICPI until symptoms return to baseline
 
Consider endocrine consultation
 
b-Blocker (e.g., atenolol, propranolol) for symptomatic relief
 
Hydration and supportive care
 
Corticosteroids are not usually required to shorten duration
 
For persistent hyperthyroidism (> 6 weeks) or clinical suspicion, work-up for Graves disease (TSI or TRAb) and consider thionamide (methimazole or PTU) Refer to endocrinology for Graves disease

G3-4: Severe symptoms, medically significant or life-threatening consequences, unable to perform ADL	
Hold ICPI until symptoms resolve to baseline with appropriate therapy
 
Endocrine consultation
 
b-Blocker (e.g., atenolol, propranolol) for symptomatic relief
 
For severe symptoms or concern for thyroid storm, hospitalize patient and initiate prednisone 1-2 mg/kg/d or equivalent tapered over 1-2 weeks; consider also use of SSKI or thionamide (methimazole or PTU).

Additional considerations
 
Thyroiditis is transient and resolves in a couple of weeks to primary hypothyroidism or normal. Hypothyroidism can be treated as above. Graves' disease is generally persistent and is due to increased thyroid hormone production that can be treated with antithyroid medical therapy. Physical examination findings of ophthalmopathy or thyroid bruit are diagnostic of Graves and should prompt early endocrine referral.
	

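### The immune-related AE count covers only events treated with steroids, immunosuppressants, hormones or insulin, although the protocol does not define these events by treatment

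*SAP*

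**What the plan says.** SAP 15.2.3.2 identifies irAEs by program: "AEs which satisfy all of the following criteria will be flagged as immune-related". In short, the criteria are:

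1. The preferred term is on a pre-selected list.
2. Onset or worsening falls between the first dose and 90 days after the last dose, ending earlier at death or before subsequent anticancer therapy.
3. The eCRF question "Were Corticosteroids, Immunosuppressants, or hormonal therapy (e.g. Thyroid) or Insulin applied" is answered yes.
4. Either no other clear etiology is recorded (4a), or a biopsy supports an immune-mediated event (4b).

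The missing-data rules open with "In the case that criteria (1) through (3) are met, and entries for condition (4) are missing". They therefore act only on events that have already passed criterion 3. No rule is given for a missing answer to criterion 3 itself.

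The planned output is any irAE, irAEs by worst grade, irAEs leading to permanent discontinuation and serious irAEs, plus a table by category. Thyroid disorders are split into "Hyperthyroidism, Hypothyroidism, Thyroiditis". SAP 6.1 keeps events of special interest in the abbreviated report.

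Protocol 6.9.2 states: "Immune-related AEs are considered AESIs". It attaches no treatment condition to that statement.

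**The concern.** Criterion 3 builds the handling of an event into its definition. Two participants with the same preferred term, the same grade and no other cause are classified differently if one was treated with a listed drug and the other was observed. Since the protocol's own guidance names observation or other drugs for several irAEs, the gate can exclude events that were managed exactly as the protocol describes.

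What is at stake is the reported frequency of a special-interest risk and its grade profile. Some excluded events may also have led to a dose hold or to stopping treatment, and these would be missing from the irAE tables, including the row for irAEs leading to permanent discontinuation.

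**Working it through.** **Step 1: logic of the rule.** Let A be the events meeting criteria 1 and 2, T those meeting criterion 3, and D those meeting criterion 4. The SAP count is A and T and D. Without the treatment gate it would be A and D. The first set is contained in the second, so the SAP count is equal or lower, never higher. An event with T answered no stays out even if 4a or 4b is fully met, because the missing-data rules start only after criteria 1 to 3.

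**Step 2: irAEs that the protocol manages without a criterion 3 drug.**

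| Event | Protocol location | Management named | Criterion 3 drug named? |
|---|---|---|---|
| Grade 1 irAEs in general | 6.9.2 | Continue and monitor, with some exceptions | No |
| Grade 1 colitis | Table A2, 2.1 | Monitoring, diet | No |
| Grade 1 pneumonitis | 6.9.2; Table A3 | Continue, monitor if indicated | No |
| Grade 1 hepatitis | Table A2, 2.2 | "No treatment is recommended for G1 liver function test abnormality" | No |
| Asymptomatic Grade 2 hepatitis | Table A2, 2.2 | Hold; steroid optional, tied to persisting elevation with symptoms | Not necessarily |
| Asymptomatic hypothyroidism, TSH < 10 | Table A4, 4.1.1 | Follow TSH and free T4 | No |
| Lower-grade hyperthyroidism | Table A4, 4.1.2 | Beta-blocker, supportive care; "Corticosteroids are not usually required to shorten duration" | Usually no |
| Grade 2 peripheral or autonomic neuropathy | Table A7, 7.3 and 7.4 | Hold; initial observation is one of two options | Only under the other option |
| Lymphopenia, up to Grade 4 | 6.9.2; Table A8, 8.5 | Hold, blood counts, screening, prophylaxis; permanent discontinuation at Grade 4 under stated conditions | No |

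The gap is widest at Grade 1 but is not confined to it.

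**Step 3: where an unflagged event still appears.**

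- Up to 30 days after the last dose it is a treatment-emergent event (SAP 9.8, 15.1). It is tabulated by system organ class, preferred term and grade (15.1.1) and, where relevant, under interruption or discontinuation (15.1.2). None of these tables carries an irAE label.
- From day 31 to day 90 it lies inside the irAE window but outside the standard on-treatment period. SAP 15.1.1 specifies only a listing for onset or worsening after that period. For untreated events the extended window therefore has no effect on the tables.
- Liver tests, creatinine and lymphocyte count are summarised by grade and shift (SAP 15.3). TSH and free T4 are only listed.

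**Step 4: size.** The documents give no irAE rate and no share of untreated irAEs, so there is no figure to reproduce. For orientation only, let p be the share of participants with an event meeting criteria 1, 2 and 4, and f the share of those with no such event treated by a criterion 3 drug. The flagged number is N × p × (1 − f), rounded, with N = 135 as planned. Both p and f are assumptions:

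| Assumed p | f = 0 | f = 10% | f = 30% | f = 50% |
|---|---|---|---|---|
| 15% | 20 (14.8%) | 18 (13.3%) | 14 (10.4%) | 10 (7.4%) |
| 25% | 34 (25.2%) | 30 (22.2%) | 24 (17.8%) | 17 (12.6%) |
| 35% | 47 (34.8%) | 43 (31.9%) | 33 (24.4%) | 24 (17.8%) |

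Example: 135 × 0.25 × 0.70 = 23.6, rounded to 24, and 24/135 = 17.8%. The grid shows how the loss scales. It does not estimate the loss in this trial.

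**The case against.** The SAP rule is explicit and programmable, and requiring treatment adds specificity. Protocol 6.9.2 sets no case-finding algorithm, and protocol 9.4.2 leaves the specifics to the analysis plan, so the two documents do not contradict each other. This stands, and it is why the four-criterion count should stay.

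Several stronger readings are tempting, and the documents do not support them:

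- **That none of the event types in the table can ever be flagged, or that the hyperthyroidism row is empty by construction.** Table A4 allows prednisone for severe hyperthyroidism. Sites might also record antithyroid drugs as hormonal therapy; the eCRF wording does not settle this. SAP 15.1 merges grade changes into one event, so a mild event that worsens and is then treated can pass. Topical steroids for Grade 1 rash (Table A1) might also count.
- **That every mild laboratory change is lost through criterion 3.** Protocol Appendix 4 excludes many isolated laboratory findings from AE reporting. Those never become AE records, and changing the irAE rule would not recover them.
- **That the events vanish from the report.** Step 3 shows that most remain visible elsewhere. What is missing is the irAE classification, and any tabulation for days 31 to 90.
- **That the reported rate will fall below the true irAE rate.** A missing 4a answer counts as an irAE, which pushes the other way among treated events, so net bias against the truth is not established.
- **That the loss can be sized from all events with a listed term.** That base ignores criterion 4, which properly removes events with another clear cause.

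The preferred-term list is not in the documents, so which of the tabled events are eligible under criterion 1 cannot be verified in detail.

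**Conclusion.** The point holds as a limit on what the irAE count means. It counts drug-treated irAEs, not irAEs as the protocol describes them, and it is equal to or lower than the same algorithm without criterion 3. The direction follows from the rule alone. The size is unknown.

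The excluded events are likely to be mainly low grade, so the reported grade profile probably leans upward. This is an expectation, not a certainty, because higher-grade lymphopenia could also be missed if its term is on the list. The conclusion assumes that at least some listed-term events recorded as AEs were managed without a criterion 3 drug, which is what the protocol's guidance describes. The issue concerns a descriptive safety summary and does not touch the primary efficacy analysis.

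**What to change.** In SAP 15.2.3.2:

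- Keep the four-criterion count and label it, in tables and report text, as drug-treated irAEs.
- Add a supportive table of events meeting criteria 1, 2 and 4 regardless of criterion 3, by category, worst grade, drug interruption and permanent discontinuation.
- In that table, give a separate row for events meeting criteria 1 and 2 whose imAE page was not completed, so that they are not counted as irAEs by default.
- State how a missing answer to criterion 3 is handled.

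The SAP already uses this approach for skin reactions, which it reports under a narrow and a broad definition (15.2.3.3). The cost is one extra table from data already collected. The downside is that the broader count will include some events of uncertain cause. No change to patient management is implied.

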15.2.3.3 TGF- β inhibition mediated skin adverse events

To identify TGF β inhibition mediated skin adverse events, MedDRA PT queries will be used to search for skin AEs of interest in the clinical database. A listing containing these pre-specified PT search terms will be generated. PTs will be compiled into categories: Narrow definition, and Broad definition. Further details (e.g. MedDRA PT queries) are regularly updated based on the current MedDRA version.

Narrow definition:

- Keratoacanthoma
- Squamous cell carcinoma of skin

Broad definition has additional PTs:

- Hyperkerathosis
- Actinic keratosis
- Basal cell carcinoma
- Lip squamous cell carcinoma
- Bowen's disease

The overall summary of TGF- β inhibition mediated skin TEAE will include the following categories for narrow and broad definition:

- All skin TEAE
- All skin TEAE by worst grade
- Skin TEAE leading to permanent treatment discontinuation
- Serious skin TEAEs

Table for skin TEAEs frequency will be provided by MedDRA PTs (including both narrow and broad definition PTs).

A listing of skin AEs will also be provided. This listing will also provide, for the AE identified from the PT list, the number of lesions, if a biopsy or an excision was done and if it confirmed the diagnosis and the lesion location coming from "TGF β MEDIATED SKIN REACTION" eCRF page.

15.2.3.4 Anemia

To identify potential anemia AEs, MedDRA PT queries will be used to search for anemia AEs of interest in the clinical database. Further details (e.g. MedDRA PT queries) are regularly updated based on the current MedDRA version.

- Anaemias NEC (HLT)
- Anaemias haemolytic immune (HLT)
- Anaemias haemolytic NEC (HLT)
- Haemoglobin decreased (PT)

A frequency tables of treatment-emergent anemia AEs and treatment-emergent related anemia AEs by worst grade (any grade, Grade ≥ 3 , Grade ≥ 4 , Grade 5), SOC and PT will be provided.

A listing of anemia AEs will also be provided with the relevant information (see description of listing in Section 15.1.1). Bintrafusp alfa related anemia will be flagged.

15.2.3.5 Bleeding events

Bleeding events are those events belonging to the MedDRA SMQ Haemorrhage terms (excluding laboratory terms). Bleeding events and trial drug related bleeding events will be summarized in a frequency table presenting SOC and PT sorted by alphabetical order. The worst grade per participant, per SOC and per PT will be reported:

Bleeding events will be summarized by the following variables:

- Any bleeding events
- Bleeding events by the worst grade
- Bleeding events leading to permanent treatment discontinuation
- Serious bleeding events

15.3 Clinical Laboratory Evaluation

Baseline and on-treatment laboratory values (including corresponding normal ranges), converted in standard unit, will be used for boxplots and shift tables.

Laboratory results will be classified according to the NCI-CTCAE criteria version 5.0 and as specified in [Appendix 2: Definition of NCI-CTCAE grading](#). Additional laboratory results that are not part of NCI-CTCAE will be categorized as follows: below normal limits, within normal limits, and above normal limits (according to the original laboratory normal ranges).

The following figures will be provided for hematology and biochemistry parameters:

- Boxplots of the laboratory values by timepoint
- Boxplots of the change from baseline by timepoint

Boxplots will display scheduled visits per protocol. In case two values are related to the same visit, the first result will be used.

Boxplots for laboratory parameters where toxicity grades are defined based on the ratio of the parameter values and the upper limit of normal (ULN) will not be displayed using the unit of measurement but instead using the ratio of the measured value over ULN. This comprises alkaline phosphatase (ALP), alanine aminotransferase (ALT), aspartate aminotransferase (AST), Activated Partial Thromboplastin Time (aPTT), bilirubin, and creatinine.

Laboratory parameters with NCI-CTC grades available

Laboratory parameters with NCI-CTC grades available will be analyzed with their respective NCI-CTC name and direction of abnormality. For parameters which are graded with both low and high values as potassium (hypokalemia/hyperkalemia), the toxicities will be summarized separately. Low direction toxicity (e.g. hypokalemia) grades at baseline and post-baseline will be set to 0 when the variables are derived for summarizing high direction toxicity (e.g. hyperkalemia), and vice versa.

The following summaries will be displayed:

- Number and percentage of participants by worst on-treatment grade (≥ 1 , ≥ 3 , ≥ 4)
- Shift in toxicity grading from baseline to highest on-treatment toxicity grade

The definitions of the NCI-CTCAE toxicity grading version 5.0 for each parameter are provided in [Appendix 2: Definition of NCI-CTCAE grading](#) of this IAP.

Table 10 NCI-CTC Gradable parameters

Parameter	Parameter code	Name in NCI-CTC	Direction of abnormality
Biochemistry			
Alanine Aminotransferase ^c	ALT	Alanine aminotransferase increased	High
Albumin	ALB	Hypoalbuminemia	Low
Alkaline Phosphatase ^c	ALP	Alkaline phosphatase increased	High
Amylase	AMYLASE	Serum amylase increased	High
Aspartate Aminotransferase ^c	AST	Aspartate aminotransferase increased	High
Bilirubin total ^c	BILI	Blood bilirubin increased	High
Corrected Calcium ^a	CA	Hypercalcemia/Hypocalcemia ^a	High/Low
Creatinine ^c	CREAT	Creatinine increased	High
Glucose	GLUC	Hypoglycemia	Low
Lipase	LIPASET	Lipase increased	High
Potassium	K	Hyperkalemia/Hypokalemia	High/Low
Sodium	SODIUM	Hypernatremia/Hyponatremia	High/Low

Parameter	Parameter code	Name in NCI-CTC	Direction of abnormality
Hematology			
Absolute eosinophils ^c	EOS	Eosinophilia	High
Absolute lymphocyte	LYM	Lymphocyte count decreased/Lymphocyte count increased	High/Low
Absolute neutrophils	NEUT	Neutrophil count decreased	Low
Hemoglobin	HGB	Anemia/Hemoglobin increased	Low/High
Leukocytes (WBC)	WBC	Leukocytosis/White blood cell decreased	High/Low
Platelets count	PLAT	Platelet count decreased	Low
Coagulation			
Activated Partial Thromboplastin Time ^b	APTT	Activated partial thromboplastin time prolonged	High
Prothrombin International Normalized Ratio ^b	INR	INR increased	High

^a based on corrected calcium (see [Appendix 2: Definition of NCI-CTCAE grading](#)).

^b reported on the "Coagulation" eCRF page.

^c baseline will be presented as Normal/Abnormal. In high direction low values will be accounted as normal and for low direction high values will be accounted as normal. For calcium, CTCAE grading is based on corrected calcium. Corrected calcium is calculated from albumin and calcium as follows based on the International System of Units (SI):

- Corrected calcium (mg/dL) = Calcium (mg/dL) – 0.8 [Albumin (g/dL)-4], or
- Corrected calcium (mmol/L) = measured total calcium (mmol/L) + 0.02 (40 – serum albumin [g/L])

Laboratory parameters with NCI-CTC grades not available

Table 11 Non-NCI-CTC Gradable Parameters

Parameter (LBTEST)	Parameter code
Biochemistry	
Bilirubin direct	BILDIR
Bilirubin Indirect	BILIND
Chloride	CL
C-Reactive Protein	CRP
Total Protein	PROT
Urea	UREA
Urea Nitrogen	BUN
Hematology	
Absolute Basophils	BASO
Absolute Eosinophils	EOS
Absolute Monocytes	MONO

Parameter (LBTEST)	Parameter code
Absolute Reticulocytes	RETI
Basophils/Leukocytes	BASOLE
Eosinophils/Leukocytes	EOSLE
Erythrocytes (RBC)	RBC
Hematocrit	HCT
Lymphocytes/Leukocytes	LYMLE
Mean Corpuscular Hemoglobin	MCH
Mean Corpuscular HGB Concentration	MCHC
Mean Corpuscular Volume	MCV
Monocytes/Leukocytes	MONOLE
Neutrophils/Leukocytes	NEUTLE
Reticulocytes/Erythrocytes	RETIRBC
Coagulation	
Prothrombin Time*	PT

* reported on the "Coagulation" eCRF page.

Calcium will be listed but not summarized

For all non-gradable parameters, the following summaries will be displayed:

- Number and percentage of participants by lowest on-treatment value (classified as normal, high, low)
- Number and percentage of participants by highest on-treatment value (classified as normal, high, low)
- Shift from baseline to highest/lowest on-treatment value (classified as normal, high, low)

In case the indirect bilirubin is not provided in the database but, at the same time point, data are provided for both total bilirubin and direct bilirubin, the missing value will be estimated using the formula: indirect bilirubin = total serum bilirubin - direct bilirubin

Separate listings of hematology (including coagulation) and biochemistry will be created. Each listing will include: participant identifier, age, sex, race, first dose date, last dose date, laboratory parameter (units), visit, date, SI value, change from baseline value, lower limit of normal, ULN, indicator of normal range (low, normal, high), toxicity grade according to NCI-CTCAE (when applicable) and highest/lowest on treatment value flag. Baseline and post-baseline values after the on-treatment period will be flagged. These listings will be sorted by participant identifier, parameter and laboratory measurement date.

The laboratory shift tables may be repeated for China sub-population.

Liver function tests

ALT, AST and total bilirubin are used to assess possible drug induced liver toxicity. The ratios of test result over ULN will be calculated and classified for these three parameters during the on-treatment period.

The number and percentage of participants within each of the following liver function categories during on-treatment period will be described:

- ALT < 3×ULN, ALT ≥ 3×ULN, ALT ≥ 5×ULN, ALT ≥ 10×ULN, ALT ≥ 20×ULN
- AST < 3×ULN, AST ≥ 3×ULN, AST ≥ 5×ULN, AST ≥ 10×ULN, AST ≥ 20×ULN
- (ALT and AST) < 3×ULN, (ALT or AST) ≥ 3×ULN, (ALT or AST) ≥ 5×ULN, (ALT or AST) ≥ 10×ULN, (ALT or AST) ≥ 20×ULN
- Total Bilirubin (TBILI) < 2×ULN, TBILI ≥ 2×ULN
- Concurrent ALT ≥ 3×ULN and TBILI ≥ 2×ULN
- Concurrent AST ≥ 3×ULN and TBILI ≥ 2×ULN
- Concurrent (ALT or AST) ≥ 3×ULN and TBILI ≥ 2×ULN
- Concurrent (ALT or AST) ≥ 3×ULN and TBILI ≥ 2×ULN and ALP > 2×ULN
- Concurrent (ALT or AST) ≥ 3×ULN and TBILI ≥ 2×ULN and ALP ≤ 2×ULN or missing

Concurrent measurements are those occurring on the same date.

Categories will be cumulative, i.e., a participant with an elevation of AST ≥ 10×ULN will also appear in the categories ≥ 5×ULN and ≥ 3×ULN.

A plot of peak ALT versus peak total bilirubin, both relative to the ULN will be provided. This eDISH plot (evaluation of drug-induced serious hepatotoxicity) will be divided into 4 quadrants by the lines through ALT ≥ 3×ULN and total bilirubin ≥ 2×ULN. The left lower quadrant is then considered normal or insignificant elevations in liver chemistries, the upper left quadrant indicates participants with possible Gilbert's cholestasis; the right upper quadrant are the possible Hy's Law participants; the right lower quadrant is possible Temple's Corollary (participants with ALT ≥ 3×ULN but not satisfying Hy's Law). Same plot will be provided for AST.

Liver function elevation may be repeated for China sub-population.

In addition, a listing of all total bilirubin, ALT, AST and ALP values for participants with a post-baseline total bilirubin ≥ 2×ULN, ALT ≥ 3×ULN or AST ≥ 3×ULN will be provided.

Urinalysis / urinalysis microscopic evaluation, hormonal tests, tuberculosis test, HIV test, serology

All test results for urinalysis /urinalysis microscopic evaluation, hormonal tests, serum and serology parameters will also be listed in dedicated listings:

- Urinalysis parameters:
 - Urinalysis full parameters: physical appearance, pH, specific gravity, protein, glucose, ketones, nitrite, leukocyte esterase, blood, urobilinogen, bilirubin, color
 - Urinalysis microscopic parameters: erythrocytes (RBC), leukocytes (WBC), epithelial cells, bacteria, crystals, casts

- Tuberculosis parameters: M. tuberculosis IFN Gamma Response by T-SPOT ELISPOT, Tuberculosis skin test (TST), M. tuberculosis IFN Gamma Response by QuantiFERON TB Gold ELISA
- Hormonal parameters: thyroxine free (Free T4), thyrotropin (Thyroid-Stimulating Hormone; TSH)
- HIV parameters: HIV test (HIV), HIV RNA viral load, CD4 Lymphocyte count (CD4LY)
- Serology parameters: hepatitis B virus (HBV), hepatitis C virus (HCV), hepatitis B DNA, hepatitis C RNA

Pregnancy test

Results for pregnancy and post-menopausal status as collected on the “Pregnancy Test” eCRF page will also be listed:

- Pregnancy parameters (serum or highly sensitive urine human chorionic gonadotropin (hCG))
- Post-menopausal status: FSH and estradiol parameters

